Randomization to the CCI dose group was removed.	
• To reduce the overall sample size of the study• The current number of participants in the [REDACTED] mg dose group is expected to provide sufficient dose-response information on the PK-PD relationship and endpoints, and is unlikely to be the dose with the optimal clinical risk-benefit balance.	Section 1.1 Synopsis; Section 1.2 Schema; Section 4.1 Overall Design; Section 4.3 Justification for Dose; Section 6.1 Study Interventions Administered, Table 8 Investigational Products; Section 6.2.3 Dose Preparation Steps, Table 9 Dose Preparation for Fixed SC Doses of CCI [REDACTED] and CCI [REDACTED] mg MEDI6570 and Placebo; Section 6.3.1 Randomization Procedure; Section 6.3.2 Blinding Procedure; Section 6.3.3 Unblinding for Interim Analysis Purposes (section deleted); Section 9.2 Sample Size Determination; Section 9.5 Interim Analyses

Table 1 Substantial Changes to the Protocol

Description of Change	Brief Rationale	Sections Affected
The number of participants was reduced from 792 to 400. CC1 	To reduce the overall sample size and improve feasibility of completion while maintaining acceptable power to inform development program decisions	Section 1.1 Synopsis; Section 1.2 Schema; Section 4.1 Overall Design; Section 9.2 Sample Size Determination
The 2 formal interim analyses were removed.	The interim analyses were administrative in nature. The full study results will be used for decision making on future development options. The study was designed to continue to completion regardless of the results of the interim analyses.	Section 1.1 Synopsis; Section 1.2 Schema; Section 4.1 Overall Design; Section 6.3.3 Unblinding for Interim Analysis Purposes (section deleted); Section 9.4.1 General Considerations; Section 9.5 Interim Analyses
The Day 405 visit (formerly Visit 16) was removed and the Day 325 visit (Visit 14) (formerly Day 334 [Visit 15]) is the new End of Study Visit	The safety follow-up visit will be performed approximately 3 months after the last dose (shortened from 6 months). CC1 	Section 1.1 Synopsis; Section 1.3 Schedules of Activities, Table 5 Schedule of Activities: Follow-up Period; Section 4.1 Overall Design

Table 1 Substantial Changes to the Protocol

Description of Change	Brief Rationale	Sections Affected

 • CCI [REDACTED] • [REDACTED] • [REDACTED] • [REDACTED] 		

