For days on or after the first dose of study treatment: date of assessment - date of first dose of study treatment + 1.

For days before the first dose of study treatment: date of assessment - date of first dose of study treatment.

For the purpose of the statistical analysis, efficacy and safety variables are allocated to the analysis visit as reported in the table below. Analysis visit is defined based on analysis day the visit occurred, visit window reported below, and using scheduled or unscheduled eCRF visits. The allocation to analysis visit windows is performed after the imputation of date of first and last doses of IP as in Section 3.1.1. Measurements with missing or partially missing dates cannot be imputed to any analysis visit.

Table 3 Scheduled analysis visit windows

Analysis visit	CSP visit name		Visit window (days)	
	After amendment 2 ^d	Before amendment 2	CTA – ECHO – Biomarkers ^a	Other parameters
Pre-treatment	Visit 2 – Visit 3		<= 1 ^b	
Day 10	Visit 4		CCI : 3 -17	3 -17
Day 29	Visit 5		Biomarkers: 21 – 37	21 – 37
Day 57	Visit 6		CCI : 49 – 65	49 – 65
Day 85	Visit 7		Biomarkers: 77 – 93	77 – 93
Day 113	Visit 8		Biomarkers: 105 – 121	105 – 121 ^c
Day 122	Visit 9		CTA: 114 – 140 CCI and biomarkers: 118-126	118 – 126
Day 141	Visit 9	Visit 10	CCI : 133 - 149	133 - 149
Day 169	Visit 10	Visit 11	CCI : 161 - 177	161 - 177
Day 197	Visit 11	Visit 12		188 - 206
Day 225	Visit 12	Visit 13	Biomarkers: 217 - 233	217 - 233
Day 253	Visit 13	Visit 14	CCI : 249-264 Biomarkers except CCI : 249 - 285 CTA, ECHO: 234 - 326	244 - 271
Day 325/405	Visit 14	Visit 16	CCI : 317 - 333/ 394 - 416	317 - 333/ 394 - 416

^a CCI , NT-proBNP, CCI CCI NT-proBNP, we will include analysis visits of pre-treatment, Day 113 and Day 253. CCI we will include analysis visits of pre-treatment, Day 10, Day 29, Day 57, Day 113, and Day 253.

^b Includes all measurements collected before or on day 1 prior to first dose of IP. If measurement is done on day 1 but time of collection is missing and per CSP parameter should be collected before first dose of study, analysis phase is “Pre-treatment”.

^c to avoid conflict between analysis visit Day 113 and Day 122, for participants who performed visit 8 before amendment 2 the visit window will be 109 – 117. For participants with missing date of reconsent for amendment 2 or who did Visit 8 before 25Jan2022 (Date of migration in EDC) the visit window will be also 109 – 117.

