3.1.3 Analysis phase windows

For the purpose of the statistical analysis, the assessments will also be assigned to the analysis phase in which they are collected as reported in [Table](#). In case of partially missing date, the imputed date will be used to assign the analysis phase.

Table 4 Analysis phase

Analysis phase	Phase window for analysis (Days)
Pre-treatment	Before first dose of study treatment (<= 1 ^(a))
On-treatment	From Day 1 ^(b) /Visit 3 up to and included 28 days after the last dose of study treatment
Follow-up	More than 28 days after the last dose of study treatment

^(a) Includes measurements collected prior day 1 or at day 1 prior to the first dose of study treatment. If measurement is done on day 1 but time of collection is missing and per CSP parameter should be collected before first dose of study, analysis phase is “Pre-treatment”.

^(b) Includes measurements collected at day 1, at the time of study treatment intake and after.

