The study day of start of the AE is calculated as the start date of the AE - date of the first dose of treatment +1 for AE started on or after day 1 and as the start date of the AE - date of the first dose of treatment for AE started before day 1. Study day of start of AE is calculated for complete dates only. Imputed dates should not be used. If one of the dates is missing or partially missing, the study day of start of the AE is missing.

All the AEs in the on-treatment and follow-up phases are considered treatment emergent adverse events (TEAEs).

The duration of AE is calculated as the end date of the AE – start date of the AE +1. Duration is calculated for complete dates only. Imputed dates should not be used. If one of the dates is missing or partially missing, the duration is missing.

The analysis will be based on as-treated population.

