4.2.10.7 Adverse events

After having assigned the AEs to the corresponding analysis phase as described in section [3.3.5.1](#), the AEs will be summarized for each treatment group and overall (total will not include placebo subjects). The AEs tables will be based on the as-treated population except the AE by ADA tables which will be based on the Immunogenicity population. Summary tables will include AEs in the on-treatment phase and AEs in the follow-up phase.

Summary tables are listed below.

An overview table containing:

- Number and percentage of subjects with any AEs
- Number and percentage of subjects with any AEs with outcome of death
- Number and percentage of subjects with any SAE (including events with outcome = death)
- Number and percentage of subjects with any AEs leading to discontinuation of treatment
- Number and percentage of subjects with any AEs leading to withdrawal from study

Subjects with multiple events in the same category are counted only once in that category.
Subjects with events in more than 1 category are counted once in each of those categories.

An overview table containing:

- Any AE
- Any AEs with outcome of death
- Any SAE (including events with outcome of death)
- Any AE leading to discontinuation of treatment
- Any AE leading to withdrawal from study

Multiple events in the same category are counted multiple times in that category. Multiple events belonging to more than 1 category are counted multiple times in each of those categories.

The following summary tables will be presented by SOC and PT:

- The number and percentage of subjects with any AEs
- The number of AEs
- The number and percentage of subjects with AEs with outcome of death
- The number of SAEs
- The number and percentage of subjects with SAEs
- The number and percentage of subjects with SAEs, assessed by investigator as possibly related to investigational product
- The number and percentage of subjects with AEs leading to discontinuation
- The number and percentage of subjects with any bleedings (all events from bleeding event form or from adverse event form with SMQ= “Haemorrhages narrow”)
- The number and percentage of subjects with any injection site reactions (all events from ISR form or from adverse event form with HLT= “Injection site reactions”)
- Overall summary of number and percentage of subjects with any AEs by ADA (anti-drug antibody category)
- The number and percentage of subjects by ADA (anti-drug antibody category)

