6 CHANGES OF ANALYSIS FROM PROTOCOL

The following analysis set populations were added: All enrolled subjects population and **CCI** analysis population.

Some parameters are no longer listed as objectives and endpoints following CSP amendment 2 (**CCI**); but summary statistics are still required for patients enrolled under CSP V1 and CSP amendment 1.

The bioanalytical test site will have access to the randomization list. A limited number of bioanalytical personnel, who will not be involved in the treatment or clinical evaluation of subjects, will be unblinded to subject treatment allocation to enable analysis of PK samples. Local SOPs will govern maintenance of the blind and information on treatment allocation will not be communicated outside of these bioanalytical personnel.

Two subjects were randomized by error **PPD** they will not be included in ITT population. Subjects did not take any dose of IP and are classified as screen failures. In the time to event analyses for **CCI** the time from randomization to Day 253 was updated by time from randomization to Day 326.

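### AE tables count crude percentages over an uncapped follow-up phase whose planned end moved from Day 405 to Day 325, so the legacy dose may be observed longer than pooled placebo

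*SAP*

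**What the plan says.** SAP 4.2.10.7 specifies the AE outputs. The first entry of the overview table is "Number and percentage of subjects with any AEs", and the other incidence tables use the same kind of count and percentage; some tables give raw event counts. On scope it says "Summary tables will include AEs in the on-treatment phase and AEs in the follow-up phase". SAP 3.1.3 (Table 4) defines the follow-up phase only by its start: "More than 28 days after the last dose of study treatment". SAP 3.3.5.1 classes every AE in either phase as treatment-emergent.

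The Protocol's Amendment 2 summary of changes shows what earlier participants were scheduled for. The Day 405 visit was dropped and Day 325 became the end-of-study visit, so safety follow-up after the last dose fell from about six months to about three. SAP 3.1.2 (Table 3) still carries both end windows for the last analysis visit: "317 - 333/ 394 - 416".

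Under Amendment 2 nobody new is randomized to the legacy dose or its matched placebo (Protocol 6.1, Table 8 footnote). SAP 4.1 pools the three placebo groups across protocol versions.

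For the time-to-event analyses, whose endpoint is redacted, SAP 6 sets one horizon: "the time from randomization to Day 253 was updated by time from randomization to Day 326". SAP 4.1.3 gives the Kaplan-Meier estimate at Day 326. No matching limit appears in the AE section.

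**The concern.** A crude percentage of participants with an event rises with the time they are watched. If one arm contains a larger share of people scheduled for the longer follow-up, its percentages rise even when the drug does nothing. Here the arms differ by design: every legacy participant was randomized under the older schedule, but only a minority of pooled placebo were.

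The planned outputs would not show whether this happened. Exposure in SAP 3.4.1 runs from first to last dose, with or without a 28-day extension, so it does not measure observation time. No table of follow-up time by arm is specified.

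The safety objective is a comparison with placebo in a study described as dose-range finding, so an artificial excess on the lowest dose would distort that arm's comparison with placebo. The arm is also small. At about 30 participants one event is 3.3% and two are 6.7%, and the common-AE table uses a threshold of more than 5% in any treatment group. One additional late case can move a preferred term into that table.

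**Working it through.** **Plan's own counts.** Protocol 1.1 gives 111 evaluable in each main dose, 27 in the legacy dose and 111 on pooled placebo: 2 × 111 + 27 + 111 = 360, as stated. Randomized: 123 per main dose and 123 on placebo, 3 × 123 = 369. At the same evaluable share (111/123 = 0.902), the legacy arm is 27/0.902 ≈ 30. The total is then about 399, against approximately 400. (The text labels 369 as active treatment, but 369 is reached only by including placebo. The result does not depend on this; taking 400 − 369 = 31 instead of 30 changes the gaps below by at most 0.1 point.)

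**Share randomized before Amendment 2.** Legacy: 100%. Placebo: Protocol Appendix I gives 1:1:1:1 under Version 1.0. The Amendment 1 ratio is printed with five terms for six groups; I read it as 3:3:3:1:1:1. Legacy to total placebo is then 1:1 under both versions, so about 30 of 123 placebo participants (24.4%) were early. The same share is expected in each main dose.

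**Mean observation time.** Let f be the share of early participants followed to Day 405. It is not given, so the range is shown. Dropout is ignored.
- Legacy: 325 + 80f days
- Placebo: 325 + 80 × 0.244 × f days

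**AE percentage with no drug effect.** Let p be an assumed risk by Day 325 under a constant hazard. Risk by Day 405 is 1 − (1 − p)^(405/325). Example at f = 1, p = 40%: legacy 1 − 0.6^1.246 = 47.1%; placebo 0.244 × 47.1 + 0.756 × 40.0 = 41.7%; gap 5.4 points.

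| f | Legacy days | Placebo days | Ratio | AE % legacy vs placebo, p = 20% | p = 40% | p = 60% | Gap over p = 5% to 80% (points) |
|---|---|---|---|---|---|---|---|
| 1 | 405 | 344.5 | 1.18 | 24.3 vs 21.0 | 47.1 vs 41.7 | 68.1 vs 62.0 | 0.9 to 6.1 |
| 0.5 | 365 | 334.8 | 1.09 | 22.1 vs 20.5 | 43.5 vs 40.9 | 64.0 vs 61.0 | 0.5 to 3.1 |
| 0.25 | 345 | 329.9 | 1.05 | 21.1 vs 20.3 | 41.8 vs 40.4 | 62.0 vs 60.5 | 0.2 to 1.5 |
| 0 | 325 | 325 | 1.00 | equal | equal | equal | 0 |

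**Other comparisons.** Main doses and placebo have the same expected early share, so the expected ratio is 1.00. All active doses combined at f = 1: (246 × 344.5 + 30 × 405)/276 = 351.1 days against 344.5, ratio 1.02.

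**If tables were split by phase.** An on-treatment column (to 28 days after last dose) would be unaffected. A follow-up column would be affected more. From Day 253 there are 72 days to Day 325 or 152 to Day 405. Legacy against placebo is then 152 vs 91.5 days at f = 1 (ratio 1.66) and 92 vs 77 at f = 0.25 (ratio 1.20).

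**The case against.** A reader might infer that the whole legacy arm was followed 80 days longer than Amendment 2 participants and that its AE rates are therefore inflated. The documents do not support that. Participants must be re-consented to the current consent form (Protocol Appendix A 3). SAP Table 3 refers to a re-consent date for Amendment 2 and to a data-capture migration on 25 January 2022. SAP 3.1.2 treats a visit as scheduled according to the version in force when it was done. Randomization before Amendment 2 does not imply follow-up to Day 405.

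The dates also point to f well below 1. If the switch took effect on 25 January 2022 (an assumption), only those first dosed by about 17 December 2020 had reached Day 405. Anyone first dosed after about 7 March 2021 had not yet reached Day 325. Later re-consent at some sites would raise f, but f = 1 is implausible.

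The size is also modest against noise. At a 40% AE risk, the standard error of a legacy-placebo difference is √(0.4 × 0.6 × (1/30 + 1/123)) ≈ 10 points, so even the upper bound is a little over half a standard error. No AE tests are planned, and the legacy arm is closed. Injection site reactions and AEs leading to discontinuation of treatment should arise mostly before Day 325. The full AE listing would allow events to be re-cut later.

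All of this limits the size; it does not remove the gap. The SAP keeps the Day 394 to 416 window, so it provides for some follow-up to Day 405. Whatever f is, the legacy arm is expected to hold about four times placebo's proportion of such participants, so the direction is predictable.

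**Conclusion.** The point holds as a possible distortion that the plan neither measures nor limits. Legacy participants may on average be observed longer than pooled placebo, and their crude AE and SAE percentages may be raised without any drug effect. The upper bound is 18% more follow-up time and about 6 percentage points. If a quarter of early participants reached Day 405, it is about 5% and at most 1.5 points; if none did, it is zero.

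These figures rest on planned rather than actual counts, the reading of the earlier allocation ratio, a constant hazard equal in all arms, and no dropout. The excess comes only from events arising after about Day 325. The imbalance is against pooled placebo as a whole; placebo participants randomized before Amendment 2 have the same expected follow-up as the legacy arm.

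The documents do not support saying that legacy rates are inflated as a fact, or that a dose trend in AEs will be hidden. Main-dose comparisons with placebo are little affected. This is a cheap improvement to the safety reporting and does not threaten the trial's main safety comparison.

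**What to change.** In SAP 4.2.10.7:

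- Add observation time by arm, and exposure-adjusted incidence (participants with an event per 100 person-years of observation), to the AE, SAE and bleeding overview tables.
- Present the summary tables with a common cut-off by study day, for example Day 326 as in the time-to-event analyses, or Day 325 plus the 7-day visit window (Day 332). List later events separately.

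Both are useful. A person-time rate corrects for unequal time only if the hazard is roughly constant, whereas the cut-off does not need that assumption.

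Do not tie the cut-off to the last dose. Under Protocol 7.1, participants who stop treatment permanently stay in the study for assessments. A last-dose limit would drop their scheduled follow-up events, SAEs and bleeding included, and would create a new imbalance if stopping differs between arms.

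The cost is SAP and table-shell wording and a little programming. The downside is that late events in early participants move from the main tables to a separate display; no data are lost.

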9.4.2.2 Secondary Endpoints

NT-proBNP

Secondary endpoint of relative change from baseline in NT-proBNP will be analyzed based on the ITT population. Relative change from baseline is defined as the ratio of the post-baseline visit value over the baseline value, expressed as a percentage. A MMRM analysis will be performed. The dependent variable is change from baseline for the log-transformed value of NT-proBNP, ie $\log(\text{post-baseline visit value}) - \log(\text{baseline value})$. The results will be back-transformed to the original scale. The model will include fixed effects of treatment group, visit, treatment group-by-visit interaction, and randomization strata, with baseline

NT-proBNP as a covariate. Repeated measures for the model will be visit within subjects. An unstructured covariance structure will be used for the repeated measures. In case the model does not converge, back-up covariance structures and other analysis solutions will be detailed in the SAP.

Secondary Endpoints Derived from Echocardiogram and CTA

Secondary endpoints that are measured by echocardiogram or CTA will be analyzed based on the Echocardiogram or CTA Analysis Population, respectively. ANCOVA analyses similar to the primary endpoint will be performed; the model will adjust for treatment group, respective baseline value, and randomization strata.

Immunogenicity Analyses

The Immunogenicity Population will be used for the immunogenicity analyses.

The number and percentage of participants with confirmed positive serum ADA to MEDI6570 will be reported by dose level. Titer data will be summarized descriptively.

The potential impact of ADA on MEDI6570 PK, efficacy, and safety will be evaluated as data allow.

PK Analyses

The PK Population will be used for the PK analyses.

MEDI6570 serum concentration data will be summarized descriptively, tabulated and plotted.

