3.3.4.2 CCI

3.3.4.3 CCI

3.3.4.4 CCI

3.3.5 Safety endpoints

3.3.5.1 Adverse events

An adverse event is the development of any untoward medical occurrence in a subject or clinical study subject administered a medicinal product and which does not necessarily have a causal relationship with this treatment. An AE can therefore be any unfavourable and unintended sign

(e.g., an abnormal laboratory finding), symptom (e.g., nausea, chest pain), or disease temporally associated with the use of a medicinal product, whether or not considered related to the medicinal product. The term AE is used to include both serious and non-serious AEs and can include a deterioration of a pre-existing medical occurrence. An AE may occur at any time, including run-in or washout periods, even if no study treatment has been administered.

Serious adverse events (SAEs) will be collected from time of signature of informed consent (either the brief, pre-screening ICF or the full, screening ICF), throughout the treatment period and including the follow-up period. All non-serious AEs will be recorded from time of first dose of study treatment, throughout the treatment period and including the follow-up period. Adverse events (AEs) will be coded with the most up to date MedDRA version. For any additional details on AE reporting please refer to the study protocol.

The AEs are assigned to the analysis phases described in section [3.1.3](#), based on the AE start date as follows:

- If the AE start date is before the first dose of treatment date, then the AE is assigned to the pre-treatment phase,
- If the AE start date is on or after the first dose of treatment date through 28 days after last dose of treatment (inclusive), then the AE is assigned to the on-treatment phase,
- If the AE start date is more than 28 days after last dose of treatment, then the AE is assigned to the follow-up phase.

If the start date of an AE is completely missing, the AE is assigned as follows:

- If the AE end date is known and is before the first dose of treatment date, then the AE is assigned to the pre-treatment phase,
- If the AE end date is completely missing or if the AE end date is on or after the first dose of treatment date no assignation can be done.

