4.2.9.1 Immunogenicity analysis

The endpoints to evaluate immunogenicity of MEDI6570 are ADA incidence and Titre. ADA and Titre are described in section 3.3.3.1. Baseline and post-baseline definitions are detailed in section 3.1.2. Tables and listings will be based on the Immunogenicity population and presented for each treatment group and overall (total will not include placebo subjects).

ADA will be summarised in IDMC reports (if data available prior to the meeting) and at final analysis using the following categories:

- ADA negative at all assessments, including baseline and post-baseline (ADA negative)
- ADA positive at baseline and/or post-baseline (ADA prevalence)
- TE-ADA positive (ADA incidence)
- Treatment-induced ADA positive
- Treatment-boosted ADA positive
- TE-ADA negative
- Both baseline and post-baseline positive
- Only baseline positive
- ADA persistently positive
- ADA transiently positive
- TE-ADA positive with maximum titre > median of maximum titres.

ADA negative is defined as having ADA negative at all assessment, including baseline and post-baseline. TE-ADA positive is defined as the sum of treatment-induced ADA positive (ADA negative at baseline and post-baseline ADA positive) and treatment-boosted ADA positive (ADA positive at baseline and boosted the pre-existing titre during the study period).

TE-ADA negative is defined as ADA positive but not fulfilling the definition of TE-ADA positive. ADA incidence is the proportion of TE-ADA positive subjects in a population.

ADA persistently positive is defined as ADA negative at baseline and ADA positive at ≥ 2 post-baseline assessments (with ≥ 16 weeks between first and last positive) or ADA positive at last post-baseline assessment. ADA transiently positive is defined as ADA negative at baseline, having at least one post-baseline ADA positive assessment and not fulfilling the conditions of ADA persistently positive.

The median of maximum titres is calculated based on the maximum titre for each ADA positive subject within each treatment group (including both baseline and post-baseline measurements).

ADA will be also reported in a listing in IDMC reports (if data available prior to the meeting) and at final analysis.

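### The AE-by-ADA tables do not separate adverse events before ADA was detected from those after it, and give no person-time, so they answer the ADA-safety question poorly

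*SAP*

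**What the plan says.** Protocol 9.4.2.2 (Immunogenicity Analyses) sets the purpose: "The potential impact of ADA on MEDI6570 PK, efficacy, and safety will be evaluated as data allow". It gives no method.

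SAP 4.2.10.7 supplies the output for safety. Among the AE summaries is "Overall summary of number and percentage of subjects with any AEs by ADA (anti-drug antibody category", with a further table of participants by ADA category. AE tables use the as-treated population "except the AE by ADA tables which will be based on the Immunogenicity population". The counting window for the AE summaries is stated once: "Summary tables will include AEs in the on-treatment phase and AEs in the follow-up phase". Events before dosing are kept out by SAP 3.3.5.1: "If the AE start date is before the first dose of treatment date, then the AE is assigned to the pre-treatment phase".

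SAP 4.2.9.1 defines the ADA categories per participant over the whole study. On one side, "ADA negative is defined as having ADA negative at all assessment, including baseline and post-baseline". On the other are "ADA positive at baseline and/or post-baseline (ADA prevalence" and, within treatment-emergent ADA, "treatment-induced ADA positive (ADA negative at baseline and post-baseline ADA positive". Eleven categories are listed. Section 4.2.10.7 does not say which of them form the table columns. It does say that its analyses go to the IDMC as well as into the final analysis.

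**The concern.** ADA status is a label fixed by everything that happens to a participant, but the AE count starts at the first dose. Suppose a participant is first positive on Day 253 and had an AE on Day 5. That AE is counted in an ADA-positive column although no ADA had been detected at the time. Treatment-induced ADA always carries some such time. Treatment-boosted ADA carries it with respect to the rise in titre.

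Follow-up is a second, separate problem. The Immunogenicity population needs only one sample, so someone who leaves the study early after negative samples is classed as ADA-negative with little time to report an AE. Table 3 of the SAP also combines final visits at Day 325 and Day 405, so both AE time and ADA sampling differ by protocol version. Longer follow-up gives more opportunity both to turn positive and to report an AE. Percentages without person-time cannot show this.

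These are the only ADA-by-safety tables in the SAP text. Table 6 of the Protocol lists hypersensitivity (including immune complex disease) and ADA among the potential risks, so the comparison will be read with those in mind.

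**Working it through.** The documents give no figure for this point, so there is none to reproduce. What follows shows size under assumptions.

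**Inputs from the documents.** Intervention 225 days plus follow-up 100 days gives 325 days (Protocol 1.1). ADA samples under Amendment 2 fall on Days 1, 29, 57, 113 and 169 (Protocol Table 4), then Days 253 and 325 (Table 5). The gaps are 28, 28, 56, 56, 84 and 72 days.

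**Assumed inputs.** ADA incidence, onset times and AE rates are not given. The hand calculation takes a rare AE, a constant background hazard, complete follow-up, ADA onset on day *d*, and a hazard ratio of 2 after onset.

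**Formulas.**
- Share of the period before onset = (d − 1)/325
- Risk ratio shown by the table = [(d − 1) + 2 × (325 − d + 1)]/325

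| Onset day d | Share before onset | Risk ratio shown |
|---|---|---|
| 29 | 28/325 = 8.6% | (28 + 594)/325 = 1.91 |
| 57 | 56/325 = 17.2% | (56 + 538)/325 = 1.83 |
| 113 | 112/325 = 34.5% | (112 + 426)/325 = 1.66 |
| 169 | 168/325 = 51.7% | (168 + 314)/325 = 1.48 |
| 253 | 252/325 = 77.5% | (252 + 146)/325 = 1.22 |

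The value without dilution would be 2.0.

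**Commoner AEs.** A risk ratio is compressed when events are common, even if ADA is present from Day 1, so that part of the gap should not be blamed on timing. With a 10% background risk, ADA from Day 1 would give (1 − 0.9²)/0.1 = 1.90. With 60% it would give (1 − 0.4²)/0.6 = 1.40. Those are the right comparators for the simulation below.

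**Simulation.** There were 400,000 participants per scenario. ADA was sampled on the post-baseline days above, with assumed ADA in 20% and AE risk of 10% or 60%. Dropout was 0 to 30%, and 0 to 50% of first AEs led to withdrawal. The planned ever/never risk ratio was compared with a rate ratio that counts events and time as ADA-positive only from the first positive sample.

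- *True hazard ratio 2, no dropout.* The planned table gives 1.48 (10% risk; comparator 1.90) and 1.24 (60% risk; comparator 1.40). The rate ratio from first positive is 1.94 and 2.00. Of first AEs in ADA-positive participants, 46% and 58% precede the first positive sample.
- *True hazard ratio 2, all scenarios.* The planned table gives 1.12 to 1.71, and the rate ratio 1.94 to 2.00.
- *No true effect.* The planned table ranges from 0.72 (10% dropout, half of first AEs leading to withdrawal, 10% AE risk) to 1.15 (30% dropout, none AE-driven, 10% AE risk). The rate ratio stays at 0.98 to 1.02.

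**The case against.** Several points against this are fair.

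- **The stakes are modest.** The Protocol promises an evaluation only as far as data permit. The tables are descriptive, and no test or decision rule in the documents uses them. This stands, and it sets the severity.
- **Timing can be checked by hand.** AEs, ADA results and ADA-positive participants are all listed, and time from first dose is derived for deaths, serious AEs and AEs leading to discontinuation. That is true, but no such check is planned.
- **The columns may be defined elsewhere.** The SAP's change log mentions separate table shells, which may name the ADA category. A reader might infer that the split is simply ever-positive against never-positive. That is the natural reading of 4.2.9.1, but 4.2.10.7 does not say so. Participants already positive at baseline have no time before ADA, so the timing problem does not apply to them unless their ADA is boosted.
- **First detection is not onset.** With gaps of up to 84 days, ADA may be present before the first positive sample. A reader might infer that AEs before that sample cannot be ADA-related. The sampling schedule does not support that. A crude cut at the first positive sample could misplace a genuine reaction, so the fix must allow for it.
- **Stopping treatment is not leaving the study.** Protocol 7.1 keeps participants under assessment after permanent discontinuation unless they withdraw consent or are lost to follow-up. Only study withdrawal shortens follow-up, and no expected rate is given.
- **A before/after split is not clean either.** Time after onset falls later in the study than time before it. If AE rates drift, the comparison with ADA-negative participants is affected. This stands as a limitation to be footnoted.

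**Conclusion.** The point holds in a limited form. As written, the AE-by-ADA tables set a whole-study ADA label against AEs counted from first dose, with no timing rule and no person-time. For treatment-induced ADA, and for the titre rise in boosted ADA, AEs before detection are counted in the ADA-positive group. A real ADA-related excess would be understated: in the illustration a true doubling appears as about 1.83 for onset at Day 57 and 1.22 for onset at Day 253. These figures assume a rare AE, constant hazard and full 325-day follow-up. If ADA appears early, the loss is small (1.91 at Day 29).

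Two stronger readings do not follow. A reader might infer that every AE from consent onward is counted, but SAP 3.3.5.1 and 4.2.10.7 leave out events before the first dose. A reader might also infer that the bias always runs towards no difference. That describes a true harmful effect. With no effect at all, unequal follow-up moved the simulated ratio to between 0.72 and 1.15.

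Severity is low, and this is a cheap improvement.

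**What to change.** In SAP 4.2.10.7:

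1. Keep the planned table and name the ADA category that forms its columns.
2. Add a companion table for participants with treatment-emergent ADA. Split AEs into those starting before and those starting on or after the first positive sample. For boosted ADA, use the first sample showing the boost.
3. Give person-time and event rates for each column and for ADA-negative participants. Person-time is essential, because restricting counts without it would bias the comparison the other way.
4. Flag AEs that start between the last negative and first positive sample as indeterminate, so that they are not silently placed before onset.
5. Footnote that onset is known only to the sampling interval (gaps up to 84 days under Amendment 2), and that time before and after onset covers different parts of the study.

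The cost is SAP wording, one derived flag and one extra table, from AE dates and ADA results already collected. Study conduct does not change, and the existing display is not lost.
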